5.2.2 Part B2

Conditional on the results from the RFS analysis from Part B1, a follow-on phase of the trial is planned that is designated as Part B2. The analysis of the B2 RFS will be supportive to the BLA to be submitted. Patients will be randomized with equal probability to a control arm for which the planned intervention is placebo, or to an experimental arm, for which the planned intervention is vaccine.

Part B2 of the trial will have co-primary endpoints of RFS followed by survival with an overall one-sided alpha of 0.025. The significance level to be used for RFS is specified to be one-sided 0.02, and the significance level to be used for the subsequent survival analysis is specified to be 0.005. (Note: The survival data from Part B1 will not be included in the analysis of survival for Part B2.) The trial is planned with power of 90% for RFS and 80% for survival.

The Part B2 trial is planned with the specific alternative RFS HR = 0.625, and the specific alternative survival HR = 0.6667 as was originally planned.

The Part B2 RFS analysis is planned using the same delayed effect specifications as were used to plan the Part B1 analysis and accrual of 800 patients in 3 years.

Simulations with 10,000 replications find a requirement for 310 RFS events and the last of these events is projected to occur 3.93 years following the start of accrual. The simulation estimate of alpha is 0.0126, the simulation estimate of power is 90.2%, and the critical RFS hazard ratio region is estimated to be ≤ 0.791 , corresponding roughly to a 26% or longer median RFS.

An interim futility and efficacy survival analysis will be performed at the time of the Part B2 RFS analysis; the final survival analysis will be done at 432 deaths. The significance levels to be used for the interim and final survival analyses are specified to be equal (not based on O'Brien-Fleming bounds) with protection of the overall one-sided 0.005 in the survival efficacy analyses. The decision to use equal significance levels at interim and final is based on increasing the chances of finding early evidence of survival efficacy.

The exact number of deaths at the time of the RFS analysis cannot be known at this time there will be an appropriate adjustment in the final efficacy significance level to be used based on the actual events at the time of the survival analysis. Assume the number of deaths at the time of the final RFS analysis is D. The information time (stated as a proportion) for the survival analysis to be done at the RFS analysis time will therefore be D/432. This proportional information time will be used to compute bounds with equal significance levels using the power method. The software suggested is SAS PROC SEQDESIGN, but other options are available.

It is projected that at the time of the analysis of RFS there will be 157 deaths in Part B2, with an information time of 36% (157 of 432). Based on the having equal significance levels for the interim and final survival analyses it is computed using SAS PROC SEQDESIGN with the power method rho specified to be 0.0003 gives significance levels of 0.002625. The survival futility analysis will be done using significance level 0.0001 and the methodology to be used for the futility analysis is described in the [Appendix “Futility Analysis.”](#)

The statistical operating characteristics for the Part B2 survival endpoint assessment requires 432 deaths and the last of these events is projected to occur 13 years following the start of accrual. The simulation estimate of alpha is 0.0030, the simulation estimate of power is 80.2%, and the critical survival hazard ratio region is estimated to be ≤ 0.764 , corresponding roughly to 31% or longer experimental arm median survival.

For the Part B2 futility survival assessment, the probability of declaring futility is estimated to be 10.7% when $HR = 1$ with critical hazard region of ≥ 1.20 , corresponding roughly to a 17% shorter experimental arm median survival. The probability of falsely declaring superiority when $HR = 1$ is 0.08%.

For the superiority interim assessment, the probability of declaring superiority when $HR = 0.6667$ is estimated to be 21.1% with critical hazard region of ≤ 0.637 , corresponding roughly to a 57% longer experimental arm median survival. The probability of falsely declaring superiority under the null hypothesis is 0.22%.

At the projected time of the final Part B2 RFS analysis or soon thereafter the trial theoretically could be opened to the sponsor because it is projected that all patients will have completed study intervention. The study is to be conducted so that neither the patient nor the clinical site workers will be aware of the study intervention actually received, and therefore all that remains to be ascertained for patients are post-recurrence interventions and vital status updates. Because patients and clinical site workers will remain blinded to the actual individual patient study intervention, the choice of post-recurrence treatments will not influence post-recurrence interventions.

Thus, the DMC will be asked to open the trial and report the outcome of the interim survival analysis to the sponsor at the time all patients are off study intervention. The DMC can decide to postpone opening the trial to the sponsor if it judges that the integrity of a complete survival efficacy evaluation is threatened by opening the trial. Additional information for the DMC will be included in a separate DMC charter.

The decision to open the trial will mean the sponsor is free to analyze the survival data from that point onward, but not perform actionable survival analysis that would lead to a conclusion of survival efficacy until the number of deaths required for the final analysis of survival events has been realized and then using the significance level adjusted for the interim analysis as described previously. Specifically, all efficacy-oriented analyses of survival between the planned survival interim analysis at the time of the RFS analysis and the final survival analysis will not be actionable.

Having access to the survival data also means the sponsor is free to perform futility analyses and act on survival futility analyses because they will not materially affect the type I error probability of the final analysis of survival efficacy. In particular, if RFS fails to meet criterion then sponsor will want to assess whether futility exists relative to survival. See the [Appendix “Futility Analyses.”](#)

See the protocol for additional details concerning the operational aspect of accrual.

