11.3 Part B

Part B of the Study is revised to include two Parts: Parts B1 and B2. Part B1 will consist of a recurrence-free survival (RFS) analysis of the first accrued 325 patients with one-sided alpha = 0.10 and 80% power; RFS is the sole primary endpoint for Part B1. Part B2 will be based on the same treatment arms as Part B1 but with 1:1 randomization of 800 patients and with one-sided alpha = 0.025 shared between RFS and Survival, and with 90% power for RFS and 80% power for survival.

At the time of the RFS analysis of Part B2, interim survival analyses of both superiority and futility will be performed. The RFS endpoint and survival (Part B2) are defined previously in this protocol.

Subjects in Parts B1 and B2 will be randomly partitioned into two arms, designated P (for Placebo) and V (for vaccine) for statistical purposes. The primary analysis will be an ITT between-arm comparison using the stratified logrank test.

The reference data are based on the control arm outcome from recent interferon trials accruing similar subjects and a projection of the stage distribution of the patients to be enrolled updated using the patients currently accrued.

Evidence of a 37.5% lower RFS hazard rate for Arm V subjects is considered clinically consequential in both Parts B1 and B2, corresponding to a hazard ratio (Arm V over Arm P) of 0.625. In Part B2 evidence of a 33.33% smaller death hazard rate for Arm V subjects is considered clinically consequential. The corresponding hazard ratio (Arm V over Arm P) is 0.6667.

Based on visual inspection of the survival Kaplan-Meier graphs from randomized adjuvant melanoma studies (10, 11) it is conjectured that there exists the possibility of a delay of the vaccine effect. The existence of a delayed effect would mean that early deaths will not differentiate between the arms and therefore the computation of the required number of events for both Parts B1 and B2 take into account the possibility of delayed effect.

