11.3.2 Part B2

Part B2 will be based on the same arms as Part B1 but with 1:1 randomization. Part B2 will have two primary endpoints (RFS and overall survival) with an overall one-sided alpha of 0.025. The significance level to be used for RFS is specified to be one-sided 0.02, and the significance level to be used for the subsequent survival analysis is specified to be 0.005. Part B2 is planned with 90% power for RFS and 80% power for survival.

Part B2 is planned with the specific alternative RFS HR = 0.625, and the specific alternative survival HR = 0.6667 as was originally planned.

The RFS analysis is planned using the same delayed effect specifications as were used to plan the Part B1 analysis and accrual of 800 patients in 3 years.

Simulations with 10,000 replications find a requirement for 310 RFS events and the last of these events is projected to occur 3.93 years following the start of accrual. The critical RFS hazard ratio region is estimated to be ≤ 0.791 , corresponding roughly to a 26% or longer median RFS.

The statistical operating characteristics for the survival endpoint assessment requires 432 deaths and the last of these events is projected to occur 13.0 years following the start of accrual. The simulation estimate of the critical survival hazard ratio region is estimated to be ≤ 0.764 , corresponding roughly to 30.1% or longer experimental arm median survival.

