There is evidence, both from melanoma trials and trials of therapeutic vaccines in other diseases, that there may be a delay in the effect of an experimental vaccine. Taking into account the possibility of a delay in effect precludes using trial size computation methods that assume proportional hazards because the proportional hazards assumption is no longer valid. Thus, some method other than the standard formulas for computing the required number of events must be used. For this trial simulations were used for delayed effect scenarios. An appendix to this document describes the simulation methodology.

For RFS analysis scenarios with delayed effect, the delay of effect is parameterized as follows: The RFS hazard ratio is assumed to be one until 1 month, followed by a period of 3 months over which the hazard ratio linearly decreases from one to 0.625, followed by a hazard ratio of 0.625 from 4 months forward.

The first year (January 2015 through December 2015) accrual experience in this study was 212 patients. The Part B1 RFS analysis being described is based on a total accrual of 325 patients which is projected to occur in June 2016.

This RFS analysis is based on one-sided alpha of 0.10 (equivalent to two-sided 0.20 for planning purposes) and statistical power of 80%. No interim analyses are planned for this RFS analysis.

Simulations with 10,000 replications based on the accrual of 325 patients as described above and the above specified alpha and power requires 126 RFS events and the last of these events is projected to occur 3.21 years following the start of accrual, that is, March 2018. The simulation estimate of alpha is

0.0887, the simulation estimate of power is 80.5%, and the critical RFS hazard ratio is estimated to be 0.792, corresponding roughly to a 26% longer median.

Overall survival for subjects in Part B1 will be followed and reported as a descriptive endpoint to the IND, as appropriate. Survival in Part B1 will be assessed as a safety outcome at the time of the final Part B1 RFS analysis. Patients enrolled in Part B1 will be followed for survival and have their vital status systematically assessed following the Part B1 RFS analysis in order to descriptively assess the long-term survival experience of Part B1 patients. The survival data from Part B1 will not be pooled with survival data from Part B2 for the formal survival analysis of Part B2.

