APPENDIX 1: ACCRUAL RATE

The simulation software used to plan the trial requires specification of the number of subjects to be accrued and the period of time over which accrual is to take place (as is usual with trial planning software). These simple specifications would generate an accrual distribution that is uniform, that is, a constant accrual rate. But since it is unrealistic to assume uniform accrual the software also allows specification of an arbitrary accrual distribution through the specification of intervals and accrual in each interval. An additional feature, and the one used in these computations, allows specification of a linear ramp time for the accrual distribution from which the accrual distribution is generated. The linear ramp time must be less than or equal to the total accrual time. Given the linear ramp time the accrual distribution is generated by assuming zero accrual at time zero and a constant accrual rate increase from time zero through the time specified by the linear ramp time, after which the accrual rate is uniform from the linear ramp time until the end of accrual. The rate of accrual increase during the ramp time and the constant accrual rate after the linear ramp time are derived from the total accrual, the total accrual time, and the linear ramp time. For example, for the computations done in this SAP the following specifications were used: total accrual time of 2 years for 960 patients and with a linear ramp time of 1 year. Figure 1 illustrates accrual rate by month.

Figure 1: Accrual Rate

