Thus, if F_1 is exponential (as usual) and F_2 is defined as above then pseudo random samples of survival times from F_1 and F_2 can be generated for specified values of λ_1 , λ_2 , d and r . These survival times can be converted to clinical trial data based on specification of accrual distribution and follow-up intervals. The net effect of delayed effect is a reduction in projected statistical power relative to no delayed effect. Specifically, events occurring prior to the time of realization of the specified effect h_A will be less differentiating than events that occur after full realization of the specified effect size h_A , and therefore only the events occurring after the time of realization of effect fully contribute to statistical power. Thus, if a trial is planned without taking into account delayed effect then the projected power of the trial will be overestimated if delayed effect is present in the data.

Statistical operating characteristics for a specific set of trial specifications, including parameters specifying a delayed effect, are estimated from replicating the generation trial data for the control arm and the experimental arm, that is, from replicates of the simulated trial data. Thus, for specified significance criteria the statistical operating characteristics of the test of the null hypothesis for superiority of the experimental intervention can be estimated using the logrank test on the simulated trial replicates. The following statistical operating characteristic estimates are most often of interest:

One-sided type 1 error probability: The proportion of replicates for which the test of the null hypothesis is rejected using the one-sided logrank test and when the experimental arm data are generated with $\lambda_2 = \lambda_1$.

- Power: The proportion of replicates for which the test of the null hypothesis is rejected using the one-sided logrank test and when the experimental arm data are generated with $\lambda_2 = h_A \lambda_1$. These estimates also can be made for interim analyses based on event time or calendar time,

and the cumulative estimates (trial-wise) are those that take into whether and when specific trial replicates meet interim analysis criteria.

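### Part B2 RFS: the simulated alpha (0.0126) and power (90.2%) do not fit the planned one-sided 0.02 stratified logrank test or the critical hazard ratio stated beside them

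*SAP*

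**What the plan says.** For Part B2, SAP section 5.2.2 fixes the level: "The significance level to be used for RFS is specified to be one-sided 0.02". Planned power is 90%. Protocol section 11.3.2 and SAP section 5.2.2 both give the event count: "Simulations with 10,000 replications find a requirement for 310 RFS events", reached at 3.93 years. The SAP adds the results: "The simulation estimate of alpha is 0.0126, the simulation estimate of power is 90.2" per cent, with a critical hazard ratio of at most 0.791.

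The primary test is stratified. Protocol section 11.3 says: "The primary analysis will be an ITT between-arm comparison using the stratified logrank test". SAP sections 6.9.1 and 6.9.2 insist on stratification. Addendum 1 changes the primary analysis set but not the test. SAP Appendix 3, which describes the simulations, says only that the null hypothesis "is rejected using the one-sided logrank test" and does not mention strata.

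Two other sets of figures have the same form:
- Part B1 (SAP section 5.2.1; 126 events, one-sided 0.10, 2:1 allocation): simulated alpha "0.0887, the simulation estimate of power is 80.5" per cent, critical hazard ratio 0.792.
- Part B2 survival (SAP section 5.2.2; 0.005 overall, two looks at 0.002625, projected at 157 and 432 deaths): "The simulation estimate of alpha is 0.0030, the simulation estimate of power is 80.2" per cent.

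No reason is given for any simulated alpha lying below its planned level. SAP Appendix 1 says that the computations used "total accrual time of 2 years for 960 patients and with a linear ramp time of 1 year", which is neither the Part B1 nor the Part B2 accrual.

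**The concern.** A simulated type I error should return the nominal level to within simulation error, unless the simulated test is conservative for a known reason. Here it is about a third below nominal, with no explanation, next to a rejection threshold that belongs to the nominal level.

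This matters because SAP section 5.2.1 sets aside the standard event formulas on account of the delayed effect. The simulations are therefore the only support for 310 and 126 events. If they do not describe the primary analysis, the stated power is not the power of the planned test. A reader also cannot tell what was simulated.

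**Working it through.** **Inputs.** From SAP section 5.2.1: stage mix 30.9/30.4/38.7%; control RFS hazards 0.154, 0.198 and 0.409 per year; hazard ratio 1 to month 1, falling linearly over 3 months to 0.625. From SAP section 5.2.2: 800 patients in 3 years, 310 events, 10,000 replications. Allocation is 2:1 in B1 and 1:1 in B2. Assumed: uniform accrual, no dropout, stage-balanced randomization, data cut at the target event.

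**1. Simulation error.** SE = sqrt(p(1−p)/10,000).
- B2: sqrt(0.02 × 0.98/10,000) = 0.0014; (0.0200 − 0.0126)/0.0014 = 5.3 SE low.
- B1: sqrt(0.10 × 0.90/10,000) = 0.0030; (0.1000 − 0.0887)/0.0030 = 3.8 SE low.
- Survival: two looks at 0.002625, correlation sqrt(157/432), give 0.0049 overall. SE = sqrt(0.0049 × 0.9951/10,000) = 0.0007; (0.0049 − 0.0030)/0.0007 = 2.7 SE low.

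**2. Critical hazard ratio.** HR = exp(−z/sqrt(E·p(1−p))), where p is the allocation fraction.
- B2, 310 events, 1:1. Level 0.02: exp(−2 × 2.054/sqrt(310)) = 0.792, which reproduces the stated 0.791. Level 0.0126: exp(−2 × 2.238/sqrt(310)) = 0.775.
- B1, 126 events, 2:1, so sqrt(126 × 2/9) = 5.29. Level 0.10: exp(−1.282/5.29) = 0.785. Level 0.0887: exp(−1.349/5.29) = 0.775. The stated 0.792 matches neither.

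**3. Simulation of the Appendix 3 model for B2.** The mean time to 310 events is 3.94 to 3.95 years against 3.93 stated, so the inputs appear to be read correctly.

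| B2, 310 events, nominal 0.02 | Alpha | Power |
|---|---|---|
| Stated in the SAP | 0.0126 | 90.2% |
| Stratified logrank (planned) | 0.019–0.021 | 92.8–93.1% |
| Unstratified logrank | 0.016–0.017 | 91–92% |

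Power of the stratified test at 0.02 by number of events: 280, 89.1%; 285, 89.9%; 290, 90.6%; 300, 91.8%. About 286 events give 90%, at roughly 3.7 years. The surplus is 310 − 286 = 24 events, and 24/286 is about 8%.

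With the 1-year accrual ramp of Appendix 1 the stratified power is 92.9%, so the power result does not depend on the accrual shape. The time becomes 4.16 years, which does not match the stated 3.93.

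**4. Does omitting stratification explain it?** Only in part. An alpha of 0.017 has SE sqrt(0.017 × 0.983/10,000) = 0.0013, so 0.0126 is still (0.0170 − 0.0126)/0.0013 = 3.4 SE low. The unstratified power remains above 90.2%.

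**5. Does a proportional-hazards formula explain it?** No. Without delay, z = |ln 0.625| × sqrt(310)/2 − 2.054 = 2.08, which is 98.1% power.

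**6. Part B1.** Stratified at 0.10 with 126 events: alpha 0.100 to 0.106 and power about 82.5%, against 80.5% stated. Unstratified: alpha about 0.095 and power about 81%. About 119 events give 80% with the stratified test. Mean time is 3.30 to 3.31 years against 3.21 stated, so this model does not fully recover the B1 inputs.

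**7. Survival.** Control death rates are not given. Assuming 0.3 to 0.4 times the RFS rates, cumulative alpha is 0.0050 to 0.0052 stratified and 0.0033 to 0.0043 unstratified. Power cannot be checked.

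**The case against.** A reader might infer that a stricter test was simulated, because the stratified test run at level 0.0126 has 90.1 to 90.3% power, almost exactly the stated figure. The documents do not support this. The stated threshold of 0.791 is that of a level-0.02 test, so the rejection rule looks right and only the realised rejection rate is low. An agreement in power does not show which test was run.

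An unstratified logrank is the candidate best grounded in the text, since Appendix 3 never mentions strata, and on stage-balanced data such a test is conservative. It moves the B2 and B1 alphas in the right direction, and the survival alpha under the assumed rates. It accounts for roughly half of the B2 power gap and most of the B1 gap. But it does not reach 0.0126, so it remains a conjecture.

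It is also tempting to say that B1 and survival show the same fault. They are weaker evidence. The B1 power gap is only about 2 points, its stated critical hazard ratio is looser than 0.10 implies (the opposite of a stricter test), and its timing is not recovered. The survival gap is 2.7 SE, and its unstratified range under assumed rates comes close to 0.0030.

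On accrual, SAP section 5.2.1 identifies 960 patients in 2 years as the original plan, and sections 5.2.1 and 5.2.2 give the current totals. The Appendix 1 sentence is a stale example, and correcting it is editorial.

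The strongest point stands in full: nothing here harms the trial's error control. The level-0.02 decision rule is intact and 310 events are enough.

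**Conclusion.** The stated B2 RFS operating characteristics are inconsistent as written. An alpha of 0.0126 does not fit the 0.02 level (5.3 SE) or the 0.791 threshold beside it. The planned stratified test at 310 events has alpha of about 0.02 and power of about 93%, nearly 3 points above the stated 90.2%; about 285 to 290 events would give 90%. The Monte Carlo and threshold checks need only figures in the SAP. The power and event figures rest on the SAP's hazards, stage mix and delay, plus uniform accrual and no dropout.

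The cause is not established. The B1 alpha and critical hazard ratio and the survival alpha support the finding but would not carry it alone.

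A reader might conclude that type I error is inflated, that the trial is underpowered, or that events should be cut. None of these follows. The discrepancy is conservative, and the surplus of about 8% does no harm to validity. The matter is the accuracy of the figures that justify the size of the pivotal part.

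**What to change.** Rerun the simulations with the planned stratified logrank at the planned levels, allocation (2:1 in B1, 1:1 in B2) and accrual. Report alpha, power, critical hazard ratio, events and timing from the same run. Restate the B2 RFS figures (expected to be about 0.02 and 93%), and restate the B1 and survival figures as the rerun gives them, including the survival control rates and any delay assumed. Say in Appendix 3 whether the simulated test was stratified, and if it was not, why. Update the Appendix 1 accrual example to the inputs actually used.

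Keep 310 and 126 events and all decision rules. The cost is one rerun and wording changes in the SAP and, where the figures are repeated, the protocol. No patients, events or analyses change.

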6.2 Protocol Deviations

All instances of protocol non-compliance will be tracked during the study and a list of protocol deviations will be finalized by a blinded Sponsor review prior to database lock. This final list of protocol deviations will be presented in a data listing and major deviations will be summarized using counts and percentages by Part A, open-label extension of Part A, and Part B.

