6.9.3 Sensitivity Analyses of Efficacy Endpoints

6.9.3.1 Sensitivity Analyses of Overall Survival (OS)

The following sensitivity analyses for OS will be performed:

- The primary OS analysis will be performed using the ATAS.
- Deaths that occur after the cutoff will not be censored.
- Clinical site homogeneity will be assessed by testing the arm by site or site class interaction. This open-ended exploration will assess homogeneity across sites using the following clumping of sites: Clinical sites with patients fewer than K patients in either arm will be pooled into a single pseudo clinical site. K will be varied in the range of 2 to 8. Classes of clinical sites will be analyzed according to characteristics such as region, type of facility, or homogeneity of medical practice for treating melanoma.
- The proportional hazard regression (PHR) will be re-run without the strata statement and with the treatment arm by stratum interaction term added to the model statement in order to assess the interaction between the treatment arms and the disease states at randomization.
- Effect modifier analyses will be performed for base attributes and particularly putatively prognostic factors, including those explored previously in the literature as well as those hypothesized to be predictive in the context of this study. These are listed subsequently. Effect modification will be assessed one factor at a time in stratified PHR models. Each factor will be analyzed as either a natural dichotomy, a dichotomized ordered categorical with cutpoint chosen based on biologic considerations, or a continuous variable dichotomized at the overall median, and possibly tertiles, quartiles or quintiles. A separate hazard ratio estimate for arm and its 95% confidence interval will be computed for each level of the categorical attribute

using contrast statements in SAS PROC PHREG. Kaplan-Meier estimates of combinations of arm by factor will be plotted on.

- Proportional hazard regression models with multiple added prognostic covariates will be estimated. The covariates to be added will include those explored previously in the literature as well as those hypothesized to be predictive in the context of this study. Interactions will also be explored for contribution to the model.

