The analysis set used for the primary analysis will be a modified ITT analysis set and will be referred to as the Full Analysis Set (FAS). The FAS is the terminology preferred in ICH Topic E9 and is the ITT analysis set with deletion of patients not initiating study intervention. The FAS is unbiased in the sense that the ITT analysis set is unbiased because this study is blinded. Analyses based on the ITT analysis set become sensitivity analyses. The rationale for this change is to conform to previously published similar

studies, the very low frequency of deletions from the ITT analysis set to create the FAS, and changes in the perception of the status of RFS relative to patient benefit.

Section 6.9.1

Add the following text in the Table where “randd” is defined:

The randomization date is that from the IVRS system.

Add the following text in the Table where “strat” is defined:

The stage used as a stratification factor in the primary analysis and related analyses is that collected from the IVRS system.

Add the following text after the paragraph before and in the Box providing template code for use of the LIFETEST and PHREG procedures:

When using SAS PROC LIFETEST quantile confidence intervals will be computed using the option CONFTYPE=LINEAR in order to invoke the Brookmeyer-Crowley method. When using PROC PHREG use the option TIES=EXACT.

Section 6.9.2

Add the following text after the first paragraph:

RFS Variable: The following variables play a role in the ascertainment of recurrence and is used for the primary analysis of recurrence as well as the recurrence sensitivity analysis to be described subsequently:

1. *The first assessment date for each patient is to be the date of randomization.*
2. *In dataset CE, variable CEOCUR (and its associated date) flags a suspicious finding on the associated date.*
3. *In dataset FA, variable FAORRES for the code variable FATESTCD with values ABCT, CHESTCT, CHESTX, and PCT are missing if not reported or flag negative (N) or positive (Y) finding for the respective radiological findings on the associated date.*
4. *In dataset FA variable FAORRES for code BMRI is missing if a brain MRI is not reported or flag negative (N) and positive (Y) brain MRI finding on the associated date.*
5. *In dataset FA variable FAORRES for code BIOPSY is missing if not reported or flag negative (N) or positive (Y) biopsy finding on the associated date.*

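### SAP 5.2.2 plans to open Part B2 survival data to the sponsor 8 to 9 years before the final OS test, but no text fixes the analysis sets before that opening

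*SAP*

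**What the plan says.** **Opening.** SAP 5.2.2 says the DMC will be asked to open Part B2 and report the interim survival result to the sponsor when all patients are off study intervention. The DMC may postpone if it judges that the survival evaluation would be threatened. Once open: "The decision to open the trial will mean the sponsor is free to analyze the survival data from that point onward". Efficacy looks before the final death count are not actionable, but the sponsor may run futility analyses and act on them. Appendix 2 tests futility on the coefficient for arm, so the access is to survival by arm. Patients and site staff stay blinded.

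**Timing.** The RFS analysis needs "310 RFS events and the last of these events is projected to occur 3.93 years following the start of accrual". For the 432 deaths of the final OS test, "the last of these events is projected to occur 13 years following the start of accrual".

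**Analysis sets.** Addendum #1, Section 4.1, makes the FAS primary. The FAS is the ITT set without patients who never started study intervention. The same text takes out of the ITT set anyone found, on review after randomization of data collected before it, to be ineligible or randomized in error. The justification is: "The FAS is unbiased in the sense that the ITT analysis set is unbiased because this study is blinded".

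**Deviations.** SAP 6.2 says "a list of protocol deviations will be finalized by a blinded Sponsor review prior to database lock". Major violations determine membership of the adequately treated analysis set (ATAS), which SAP 4.4 calls supportive. SAP 6.9.3.1 lists, among the sensitivity analyses, "The primary OS analysis will be performed using the ATAS".

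**The concern.** OS is one of the two Part B2 primary endpoints. Two rules that settle who is analysed draw their protection from blinding, while SAP 5.2.2 plans to end the sponsor's blinding years before the final OS lock. For that lock, an opened sponsor cannot carry out the review in SAP 6.2 as worded, and the Addendum's reason for calling the FAS unbiased no longer applies to it.

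The Addendum's removal rule reaches the primary test. It has no closing date and names nobody to decide. An eligibility question reopened after opening could be settled by people who know each arm's survival. The one-sided 0.005 for OS assumes that membership does not depend on the result. An ITT analysis would not expose the problem, because under the Addendum the removal is made from the ITT set itself.

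The Addendum was written ahead of an unblinding with a January 2019 cutoff, but its Section 4.1 text is not limited to Part B1. It also shows that a primary population can change late. That change relied on the study still being blinded, and a similar change in B2 after opening could not.

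**Working it through.** **1. The plan's own figures**

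- *RFS timing.* Inputs are the control hazards 0.154, 0.198 and 0.409 per year with stage mix 30.9/30.4/38.7% (SAP 5.2.1), hazard ratio (HR) 0.625 after the stated delay, "accrual of 800 patients in 3 years", and 1:1 allocation ("Patients will be randomized with equal probability to a control arm"). Expected events reach 310 at 3.95 years with uniform accrual, against 3.93 stated. A 1-year accrual ramp gives 4.16 years.
- *Final OS critical HR.* exp(−2z/√D) with z = 2.791 (one-sided 0.002625) and D = 432 gives 0.764, as stated.
- *OS alpha.* Two looks at 0.002625 with information 157/432 give an overall one-sided level of 0.0049, within 0.005.
- *Not reproducible.* The 432 deaths and 13 years cannot be derived, because control survival rates and any survival delay are not given. Proportional hazards with 80% power at 0.002625 would need 322 deaths (Schoenfeld) or 331 (Freedman). I take 432 and 13 as stated.

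**2. The interval**

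- From the RFS analysis: 13 − 3.93 = 9.07 years.
- From the last planned dose of the last patient: 13 − (3 + 2) = 8.0 years.
- Deaths still to come after the projected interim: 432 − 157 = 275, or 64%.

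The two starting points differ because SAP 5.2.2 expects all patients to be off treatment at or soon after the RFS analysis. With 3-year accrual and 24 months of dosing, the last patient finishes at 5.0 years. At 3.93 years about 36% (uniform accrual) to 43% (1-year ramp) are within 24 months of randomization. Those statements need reconciling.

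**3. What is and is not fixed before opening**

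| Item | Fixed independently of the result? |
|---|---|
| Death, stratified logrank test, one-sided p, alpha, 432 deaths | Yes (SAP 5.2.2, 6.9.1) |
| Stage strata, randomization date | Yes, from the IVRS (Addendum) |
| Started study intervention or not (FAS step) | Yes, an objective fact settled early |
| Ineligible or randomized-in-error removals | Limited to pre-randomization data; no closing date, no named decider |
| Major-deviation list | Sponsor review; affects the ATAS only |

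**4. Leverage of a few removals**

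A one-sided p of 0.005 is z = 2.576, and 0.002625 is z = 2.791, so crossing needs a shift of 0.215. A rough bound per vaccine-arm death removed is 0.5/√(432/4) = 0.5/10.39 = 0.048. Five give 0.24, so z = 2.816 and p = 0.0024. This ignores the expected-event contribution that leaves with each patient, so it suits only the earliest deaths.

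Simulation removes that approximation: 800 patients 1:1, uniform 3-year accrual, 432 deaths, no delay, unstratified, true HR about 0.78. The control death hazard is an assumption, 0.08 per year. With HR 0.6667 and uniform accrual, a hazard of 0.082 puts the 432nd death at 13 years. Removing five vaccine-arm deaths from a result at p = 0.005:

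| Which five | Shift in z | p after |
|---|---|---|
| Earliest deaths | 0.256 | 0.0023 |
| Random deaths | 0.17 | 0.0031 |
| Random deaths after the 157th | 0.13 | 0.0034 |

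Hazards of 0.07 and 0.09 give the same shifts to two decimals. Only the first row crosses 0.002625.

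Under HR = 1 with hazard 0.075 (4,000 replicates), the final-look one-sided error is about 0.002. It rises to about 0.0045 if the 4 earliest-dying vaccine patients are removed, and to about 0.010 if 8 are (2% of that arm). These are worst-case selections.

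**The case against.** The strongest reply is that little is left to decide. Removals rest only on pre-randomization data. Accrual ends at 3 years, and the RFS analysis needs the same sets before any opening, so a blinded review at that lock would settle them. SAP 5.2.2 itself says that only later treatments and vital status then remain to be collected, from sites that stay blinded. The DMC can also hold the trial closed for exactly this reason, and its charter, which is not among the documents, may say more.

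Most of this stands, and it limits the size of the problem. But no sentence carries the sets from the RFS lock to the OS lock, none closes the Addendum's removal rule, and the DMC's discretion sets no condition on populations if it does open. That only vital status remains is therefore an expectation, and no rule enforces it.

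Some stronger readings are tempting and are not supported:

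- *The deviation list shapes the primary OS test.* Read alone, the ATAS sentence in SAP 6.9.3.1 suggests so, but it is a sensitivity analysis and SAP 4.4 calls the ATAS supportive.
- *Strata or loss-to-follow-up coding stay open to influence.* Stage comes from the IVRS. The SAP code censors both follow-up categories, so reclassifying a patient neither adds nor removes a death. Only a censoring date could move.
- *The sponsor makes the eligibility removals.* The Addendum names nobody. The gap is that it leaves this open.

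**Conclusion.** The point holds in a limited form. SAP 5.2.2 plans sponsor access to B2 survival by arm 8.0 to 9.1 years before the final OS test, subject to DMC postponement. The Addendum's eligibility removals, which reach the primary FAS, are not closed before that access and are defended by a blinding the sponsor would no longer have. The SAP 6.2 conflict is real but touches only the ATAS.

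The scope for bias is narrow. A reader might infer that any five late exclusions would turn a failed OS test into a success. The calculation does not support that: five random or post-interim vaccine-arm deaths leave p at about 0.003, above 0.002625, and only the five earliest cross. Even that needs five ineligible vaccine patients and no offsetting placebo patients, and a starting p of 0.005 chosen for illustration. The figures rest on an assumed control hazard of 0.07 to 0.09 per year, no delay and no stratification. They show leverage and predict nobody's conduct. Because the endpoint is primary and the blinded step cannot be done as written at the OS lock, the wording should be changed.

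**What to change.** Add to SAP 5.2.2, SAP 6.2 and Addendum Section 4.1:

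- Before any opening of Part B2 to the sponsor, a blinded review finalizes and archives ITT and FAS membership (including every eligibility and randomized-in-error removal), ATAS membership and the major-deviation list.
- These are used unchanged for the final OS test.
- After opening, only new death and last-known-alive dates enter the primary OS dataset.
- Any later change of population is labelled post hoc and reported as a sensitivity analysis.

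The DMC charter should make the archived sets a condition of opening.

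The cost is SAP and charter wording and one blinded review done before opening. The 432 deaths, the one-sided 0.005 and the critical HR of 0.764 do not change. The downside is that an ineligibility discovered late stays in the primary set and can be examined only in a sensitivity analysis.
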